## 9.2 Discussion of Study Design

### 9.2.1 Rationale for Subject Population

Perampanel has been extensively evaluated in multiple Phase 3 studies, predominantly in a refractory patient population. The Phase 3 study protocols specified that subjects should have failed therapy with at least 2 AEDs and currently be administered 1 to 3 concomitant AEDs. The current study aims to obtain data in earlier-onset subject groups who require initial AED therapy either with monotherapy or a 1st adjunctive therapy. These data will complement the extensive data that are already available for perampanel and will support its use in early-onset patients.

### 9.2.2 Rationale for Efficacy Endpoints

According to “Guideline on clinical investigation of medicinal products in the treatment of epileptic disorders” provided by European Medicines Agency, in an adjunctive study, the primary endpoint should dichotomize the data into responders/non-responders, where responders are subjects who obtained at least a certain pre-defined percentage reduction of seizure frequency (Steinhoff, et al., 2013). Retention rate is commonly used for studies resembling real life, as it represents the result of satisfactory efficacy and safety.

The primary efficacy endpoint is the retention rate of perampanel when given as monotherapy or 1st adjunctive therapy in subjects with POS or PGTCS.

### 9.2.3 Rationale for Prohibited/Restricted Concomitant Drug/Therapy

For the evaluation of perampanel as 1st adjunctive therapy, 1 concomitant AED is permitted, if it has been administered at a stable dose for 8 weeks before Visit 2 (Week 0). Details of prohibited/restricted concomitant drugs and other therapy are presented in [Section 9.4.7](#).

## 9.3 Selection of Study Population

Approximately 125 subjects will be entered at up to approximately 25 sites in the US. (revised per Amendment 01) Subjects who do not meet all of the inclusion criteria or who meet any of the exclusion criteria will not be eligible to receive study drug.

### 9.3.1 Inclusion Criteria

Subjects must meet all of the following criteria to be included in this study:

1. Subjects will be male or female and no younger than 4 years of age and be able to swallow perampanel tablets. (revised per Amendment 01)
2. Subjects must have a diagnosis of epilepsy with POS with or without SGS, or with PGTCS. Either of the following must have occurred to support an epilepsy diagnosis: (revised per Amendment 01)
  - a. At least 2 unprovoked (or reflex) seizures occurring greater than 24 hours apart

- b. 1 unprovoked (or reflex) seizure with EEG evidence of seizures
3. Subjects who receive perampanel as a 1st adjunctive therapy must currently have been treated with stable doses of monotherapy with an AED for 8 weeks prior to Visit 2 (Week 0), have not previously received adjunctive AED treatment, and must, in the investigator's judgement, be in need of initial adjunctive therapy after failure to control seizures with AED monotherapy, at the optimal dose and duration. (revised per Amendment 01)
4. Subjects who receive perampanel as monotherapy, who were newly diagnosed (treatment naïve), following the defined diagnosis of epilepsy. (revised per Amendment 01)
5. Subjects who are currently receiving monotherapy treatment may receive perampanel as monotherapy if, in the investigator's judgment, the subject may benefit from a change in monotherapy treatment. Subjects must not have previously received adjunctive AED treatment.
6. If antidepressants or antianxiety drugs are used, subjects must be on a stable dose regimen of these drugs during the 8 weeks before Visit 2 (Week 0).

### 9.3.2 Exclusion Criteria

Subjects who meet any of the following criteria will be excluded from this study:

1. Subjects should not have previously received or currently be receiving perampanel.
2. Females who are breastfeeding or pregnant at Screening or Baseline (as documented by a positive beta-human chorionic gonadotropin [ $\beta$ -hCG] [or human chorionic gonadotropin (hCG)] test with a minimum sensitivity of 25 IU/L or equivalent units of  $\beta$ -hCG [or hCG]); a separate baseline assessment is required if a negative screening pregnancy test was obtained more than 72 hours before the 1st dose of study drug.
3. Females of childbearing potential who:
  - Within 28 days before study entry, did not use a highly effective method of contraception, which includes any of the following:
    - Total abstinence (if it is their preferred and usual lifestyle)
    - An intrauterine device or intrauterine hormone-releasing system
    - An oral contraceptive (with additional barrier method if using contraceptive containing levogesterol); subject must be on a stable dose of the same oral contraceptive product for at least 28 days before dosing and throughout the study and for 28 days after study drug discontinuation
    - Have a vasectomized partner with confirmed azoospermia
  - Do not agree to use a highly effective method of contraception (as described above) throughout the entire study period and for 28 days after study drug discontinuation

For sites outside of the EU, it is permissible that if a highly effective method of contraception is not appropriate or acceptable to the subject, then the subject must agree to use a medically acceptable method of contraception, ie, double-barrier methods of contraception such as condom plus diaphragm or cervical/vault cap with spermicide.

NOTE: All females will be considered to be of childbearing potential unless they are postmenopausal (amenorrheic for at least 12 consecutive months, in the appropriate age group, and without other known or suspected cause) or have been sterilized surgically (ie, bilateral tubal ligation, total hysterectomy, or bilateral oophorectomy, all with surgery at least 1 month before dosing).

4. Presence of or previous history of Lennox-Gastaut syndrome
5. Presence of non-motor simple partial seizures only
6. A history of status epilepticus within 1 year before Screening Visit (Visit 1)
7. Subjects on antipsychotics or who have psychotic disorder(s) or unstable recurrent affective disorder(s) with a history of attempted suicide within 1 year before Screening Visit (Visit 1)
8. Presence of a progressive central nervous system (CNS) disease, including degenerative CNS diseases and progressive tumors
9. Concomitant use of barbiturates (except for seizure control indication and premedication for EEG) and benzodiazepines (except for seizure control indication) within 8 weeks prior to Visit 2 (Week 0)
10. Use of intermittent rescue benzodiazepines (ie, 1-2 doses over a 24-hour period is considered a 1-time rescue) 2 or more times in the 8 week period prior to Visit 2 (Week 0)
11. Severe renal insufficiency (defined by estimated glomerular filtration rate of <30 mL/min) or subjects who receive hemodialysis
12. Evidence of clinically significant disease (eg, cardiac, respiratory, gastrointestinal, renal disease, hepatic disease) that in the opinion of the investigator(s) could affect the subject's safety or study conduct

NOTE: Stable elevation of liver enzymes, alanine aminotransferase and aspartate aminotransferase due to concomitant medication(s), will be allowed if they are less than 3 times the upper limits of normal.

13. Hypersensitivity to perampanel or any excipients
14. Subjects with rare hereditary problems of galactose intolerance, the Lapp lactase deficiency or glucose-galactose malabsorption
15. Subjects who are participating in other interventional clinical trial
16. Subject who are judged to have inadequate cognitive ability for participation in the study (intelligence quotient [IQ] <80 or investigator judgment)
17. Any suicidal ideation with intent with or without a plan, at the time of or within 6 months of Screening, as indicated by answering "Yes" to questions 4 and 5 on the Suicidal Ideation section of the Columbia-Suicide Severity Rating Scale (C-SSRS)
18. Any lifetime suicidal behavior based on the C-SSRS
19. Concomitant use of any form of cannabidiol (CBD) (revised per Amendment 01)
20. Planned brain surgery during study participation (revised per Amendment 01)

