It is the responsibility of the investigator to review the results of the C-SSRS in all subjects and determine if any result constitutes an AE. Medical and scientific judgment should be exercised in deciding whether an isolated suicidality rating scale response should be classified as an AE.

All AEs must be followed for 28 days after the subject's last dose, or until resolution, whichever comes first.

Every effort must be made by the investigator to categorize each AE according to its severity and its relationship to the study treatment.

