**9.5.1.6.9 COLUMBIA-SUICIDE SEVERITY RATING SCALE**

An assessment of suicidality will be performed using the C-SSRS at the visits designated in the Schedule of Procedures/Assessments (Table 4). The C-SSRS will be administered to patients 6 years of age and older. Subjects under 6 years of age will be clinically monitored for suicidality. (revised per Amendment 01)

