### 5.2.3 Protocol Deviations

Subjects with major protocol deviations will be listed. These may include:

- Recruitment of a subject who did not satisfy the inclusion/exclusion criteria
- Subjects who took excluded medication
- Overdose of Investigational Products of 120% or above between 2 consecutive visits or Study Medication compliance <80% between two consecutive visits.
- Continuation of treatment with Study Medication after a treatment related withdrawal event
- Unauthorized dose adjustment during Titration Period and Maintenance Period.

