### **Columbia Suicide Severity Rating Scale (C-SSRS)**

Suicidality will be assessed using the C-SSRS and summaries will include the incidence of suicidal behavior and suicidal ideation for subjects 6 years of age and older. Scoring of the C-SSRS will be performed as suggested by the C-SSRS Columbia website:

<http://www.cssrs.columbia.edu>.

The following summaries will be presented for the treatment duration (Titration Period and Maintenance Period).

- Number (percentage) of subjects with any treatment-emergent report of suicidal behavior, suicidal ideation, and suicidality (suicidal behavior and/or ideation) will be displayed. A treatment-emergent report of suicidal behavior, suicidal ideation, or

suicidality is an answer of 'Yes' to any question in the respective category during the treatment duration.

- Shift from baseline to the maximum suicidal ideation severity rating (0=no ideation present to 5=active ideation with plan and intent) in the treatment duration will assess worsening of suicidal ideation. Any score greater than 0 indicates the presence of suicidal ideation while a score of 4 (active suicidal ideation with some intent to act) or 5 (active suicidal ideation with specific plan and intent) can be used to indicate serious suicidal ideation.

Descriptive statistics and changes from baseline will be presented by visit for the suicidal ideation intensity score and the suicidal ideation severity rating (treated as a continuous variable) to assess change in suicidal ideation over time. The suicidal ideation intensity score ranges from 0 to 25 and is the sum of the 5 intensity items.

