## 7 CHANGES IN THE PLANNED ANALYSES

Due to recruitment challenges, enrollment was terminated before reaching the planned sample size. Thus, there will not be enough sample size to calculate the 95% CIs. Analysis of BDI-II scale is added as an exploratory analysis.

There are no other changes to the analysis in this statistical analysis plan compared to the protocol. Any future changes to the analysis will be documented separately and will be addressed in the Clinical Study Report.

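### Exclusion 17 covers suicidal intent whether or not there is a plan, but its C-SSRS trigger can be read as needing both answers: a minor wording error in a safety criterion

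*Protocol*

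**What the plan says.** Item 17 of Protocol 9.3.2 has two parts. The first names who is excluded: "Any suicidal ideation with intent with or without a plan", present at Screening or within the 6 months around it. The second says how this is recognized on the C-SSRS, by a Yes "to questions 4 and 5 on the Suicidal Ideation section". The Synopsis gives the criterion in the same terms.

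The Protocol does not say what questions 4 and 5 ask. The nearest description is in SAP 5.6.4, under the C-SSRS heading, which marks serious ideation with the words "while a score of 4 (active suicidal ideation with some intent to act) or 5 (active suicidal ideation with specific plan and intent".

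Item 18 is the neighboring suicidality criterion: "Any lifetime suicidal behavior based on the C-SSRS". In the Protocol's schedule (Table 4), the eligibility check and the C-SSRS both appear at Screening and again at Visit 2. The age limit is in Protocol 9.5.1.6.9: "The C-SSRS will be administered to patients 6 years of age and older".

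**The concern.** The two parts of item 17 should pick out the same subjects. If the second part needs a Yes to both questions, and question 5 carries the plan, then the test detects only intent with a plan. Intent without a plan is named in the first part and missed by the second.

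This is a patient-safety criterion. A site that turned the C-SSRS part into a checklist would pass a subject whom the sentence means to keep out. Later, whoever lists eligibility deviations would have to decide whether such a subject was one, and the two readings give opposite answers.

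**Working it through.** There is no figure in the plan to reproduce. The check sets the two parts of the criterion side by side for each answer pattern.

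**Inputs**
- Population to be excluded: ideation with intent, plan or no plan (Protocol 9.3.2 item 17, first part; Synopsis).
- Trigger: Yes to questions 4 and 5 (same item, second part).
- Level 4 is some intent to act; level 5 is specific plan and intent (SAP 5.6.4). The SAP is used only for these definitions.
- Assumption: questions 4 and 5 are the items behind levels 4 and 5. The C-SSRS form is not in the documents, so this cannot be confirmed.

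**Comparison**

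| Q4 | Q5 | Meaning on the SAP definitions | First part excludes? | Trigger, both needed | Trigger, either suffices |
|---|---|---|---|---|---|
| No | No | no intent reported | no | no | no |
| Yes | No | intent, no specific plan | yes | **no** | yes |
| Yes | Yes | intent with specific plan | yes | yes | yes |

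The first part excludes 2 of the 3 patterns. The trigger that needs both answers excludes 1 of 3. The difference is 2 − 1 = 1 pattern, Yes/No. With either answer sufficient, the trigger agrees with the first part in all three rows.

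No/Yes is left out of the count. Level 5 already includes intent, and without the form one cannot tell whether that pattern can be recorded. These are counts of logical patterns and say nothing about how many subjects fall in each.

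**Does another rule catch Yes/No?**
- Item 18 concerns suicidal behavior, not ideation alone.
- Item 7 concerns antipsychotic use, psychotic disorder, or unstable affective disorder with attempted suicide. It does not name ideation alone.
- Item 12 leaves clinically significant disease to the investigator's opinion. Its examples are somatic and it does not mention ideation.
- The investigator judgment in item 16 is about cognitive ability.
- Protocol 9.5.1.6.1 has the investigator "review the results of the C-SSRS in all subjects and determine if any result constitutes an AE". That is a decision about adverse events, not eligibility.

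Some of these might lead a careful investigator to exclude the subject. None does so by rule.

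**The case against.** The strongest reply is that the sentence resolves its own ambiguity. On the SAP's definitions, question 4 captures intent without a specific plan and question 5 captures intent with one, so the two questions match the two halves of the opening clause. Read that way, the wording lists the two relevant items, and a Yes to either is enough. Needing both would leave the mention of intent without a plan with no effect. This stands: it is the better reading of the whole sentence. It does not make the wording safe, because the text does not say that either answer is enough, and the C-SSRS answers are presented as the working test.

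Other limits also stand:
- No worksheet, eCRF check or site instruction in the documents shows that anyone applied the both-answers reading.
- The investigator may withdraw a subject for safety at any time (Protocol 9.3.3.2), and the C-SSRS is repeated at each on-site visit through Week 52. Neither is an eligibility rule, but both limit the consequences of a misreading at entry.
- The match between questions and levels is plausible but unverified.

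A reader might infer that the Protocol permits enrolling subjects with intent but no plan. It does not, because the opening clause excludes them. A reader might also take the *or* in SAP 5.6.4 as a competing eligibility rule. It is not one: that passage describes how post-baseline ideation is summarized.

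**Conclusion.** This is a minor wording error in a safety criterion. Under the reading that needs both answers, the C-SSRS trigger misses one of the three answer patterns, intent without a plan, which the opening clause already excludes. The conclusion rests on questions 4 and 5 being the items behind levels 4 and 5.

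Severity is low. SAP section 7 reports that "enrollment was terminated before reaching the planned sample size", so rewording the criterion affects no future subject. What remains is the deviation listing in SAP 5.2.3, where major deviations may include "Recruitment of a subject who did not satisfy the inclusion/exclusion criteria", and the use of eligibility violation as a withdrawal reason for any subject still on treatment. The documents do not say whether there are any. Neither analysis set in SAP 5.2.1 removes subjects for deviations, so listing a subject as a deviation changes no endpoint estimate.

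One might go further and infer that ineligible subjects were enrolled. The documents do not support that. They give no C-SSRS results, and the number affected may be zero.

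**What to change.** In Protocol 9.3.2 item 17 and in the Synopsis, replace the connector so that the trigger reads *question 4 or question 5*.

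For the deviation listing under SAP 5.2.3, state before the list is compiled that a Yes to either question at Screening counts as not meeting item 17. Apply this to subjects aged 6 years or older. Younger subjects are monitored clinically and have no C-SSRS to check. The documents do not give the recall period of the Screening form, so the check covers whatever period that form recorded.

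The cost is one word in two places and one rule applied to Screening data already scheduled for collection. It needs no new data, no added analysis and no change to the sample size.

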### 9.3.3 Removal of Subjects from Therapy or Assessment

#### 9.3.3.1 Scheduled Termination

Subjects will be considered to have completed the Titration Period after up to 13 weeks of titration treatment and completion of the Visit 4 (Week 13) visit procedures. (revised per Amendment 01) Subjects who have completed the Titration Period will enter the Maintenance Period. Subjects will be considered to have completed the Maintenance Period after 39 weeks of maintenance treatment and completion of the Visit 7 (Week 52) visit procedures. Upon completion of the Titration Period, the Maintenance Period, and the Follow-Up Period, and after resolution of any AEs that may be present on the last visit, the subject will be considered to have completed the study.

#### 9.3.3.2 Withdrawals

Subjects who were administered at least 1 dose of study drug but could not participate in the study are classified as 'withdrawals'. The investigator may withdraw the subject from the study at any time for safety or administrative reasons. The subject may stop study drug or withdraw from the study at any time for any reason.

Reasons for withdrawal are as the following:

- Withdrawal of informed consent
- AE(s) requiring discontinuation of study therapy
- Eligibility violation
- Lack of efficacy
- Administration of prohibited medications
- Lost to follow-up
- Unable to continue the study in the investigator's judgment

The investigator will make every reasonable effort to follow up subjects for any AEs. He/she will use all possible ways to communicate (phone call, letters, and visit to home) with the subject. The reason for withdrawal should be documented on the eCRF. Final assessments of withdrawn subjects should be conducted and documented as described in [Section 9.6.1](#). Withdrawn subjects will not be allowed to re-enter the study.

## 9.4 Treatment

### 9.4.1 Treatment Administered

Perampanel will be administered to subjects during each study period. Tablets at the assigned dose strength will be taken orally once daily before bedtime. At the beginning of the Titration Period, oral perampanel will start at a dose of 2 mg QD. Doses of perampanel will then be up-titrated in increments of 2 mg/day at no less than 2-week intervals according to the investigator's judgment. At the 4 mg dose (Week 4, telephone call, Visit 3), the investigator will confirm whether further dose escalation is needed based on subject response

and tolerability. The investigator may adjust dosing further or leave the subject at 4 mg. The maximum dose is 12 mg. Subjects who are taking concomitant AEDs that are known cytochrome P450 (CYP) enzyme inducers (eg, phenytoin, carbamazepine, oxcarbazepine, eslicarbazepine) which shorten the half-life of perampanel, can undergo up-titration in 2-mg increments at intervals of at least 1 week.

The study drug will be dispensed to each subject or guardian/legally authorized representative at Visit 2 (Week 0), Visit 4 (Week 13), Visit 5 (Week 26), and Visit 6 (Week 39). Sites must enter the perampanel dosing information into the IRT system on Weeks 2, 4, 6, 8, 10, and 12 to track subject dosing. (revised per Amendment 01)

Tablet(s) cannot be split, broken or crushed prior to administration, and should be administered whole at bedtime.

#### 9.4.2 Identity of Investigational Product

- Perampanel will be supplied by the sponsor.
- Product name/manufacturer: Fycompa/Eisai Inc.
- Formulation/drug appearance is presented in [Table 2](#).
- Storage condition: 20°C to 25°C (68°F to 75°F) with excursions permitted at 15°C to 30°C (59°F to 86°F).

**Table 2 Formulation/Drug Appearance**

Tablet strength	Description
2 mg	Orange, round, biconvex, film-coated tablets
4 mg	Red, round, biconvex, film-coated tablets
6 mg	Pink, round, biconvex, film-coated tablets
8 mg	Purple, round, biconvex, film-coated tablets
10 mg	Green, round, biconvex, film-coated tablets
12 mg	Blue, round, biconvex, film-coated tablets

##### 9.4.2.1 Chemical Name, Structural Formula of E2007

- Test drug code: E2007
- Generic name: Perampanel
- Chemical name: 2-(2-oxo-1-phenyl-5-pyridin-2-yl-1,2-dihydropyridin-3-yl)benzotrile
- Molecular formula:  $C_{23}H_{15}N_3O$
- Molecular weight: 349.38 (anhydrous)

#### 9.4.2.2 Comparator Drug

Not applicable.

#### 9.4.2.3 Labeling for Study Drug

Test drug will be labeled in accordance with text that is in full regulatory compliance with each participating country and is translated into the required language(s) for each of those countries. Perampanel (E2007) is a Schedule III Controlled Drug Substance in the United States (US) and will be labeled as such for US sites.

#### 9.4.2.4 Storage Conditions

Perampanel will be stored in accordance with the labeled storage conditions. Temperature monitoring is required at the storage location to ensure that the perampanel is maintained within an established temperature range, 20°C to 25°C (68°F to 75°F) with excursions permitted at 15°C to 30°C (59°F to 86°F).

